11.2 Adverse Events

Only SAEs and AESIs will be recorded in this study. Treatment-emergent SAEs and AESIs, defined as AEs that started [or worsened] on or after the start of IP infusion, will be summarized. All captured AEs regardless of whether they were treatment-emergent or not will be listed. Where AE start dates and/or times are missing or partially missing, AEs will be assumed to be treatment-emergent, except if the partial start dates and/or times or the AE end date and/or time indicate that the AE started before the first administration of IP (see Table 3).

Table 3 TEAE Assignment in Case of Missing AE Start Date Elements

Missing Elements of AE Start	Rule	
Regardless of any missing information for AE start: AE end date / time < IP start date / time		non-TEAE
Otherwise (ie, if AE end date / time \geq IP start date / time)		
- All		TEAE
- Day and month	AE start year \geq IP start year	TEAE
	AE start year < IP start year	non-TEAE
- Day	AE start month / year \geq IP start month / year	TEAE
	AE start month / year < IP start month / year	non-TEAE
- Time	AE start date \geq IP start date	TEAE
	AE start date < IP start date	non-TEAE

AE = adverse event; IP = investigational product; TEAE = treatment-emergent adverse event

If AE start dates or end dates are missing or partially missing for an AE, no duration will be calculated. If for a TEAE the relationship to study treatment is missing the worst case will be assumed for summarizing analysis (ie, the relationship to study treatment will be assumed to be “Yes”). No imputation will be done in case of missing study treatment relationship for non-treatment emergent AEs. No other imputations for missing AE information will be done.

AEs will be coded using the MedDRA dictionary, version 27.1 or later. The observation period for the reporting of AESIs and SAEs for an individual subject will start at the time of

randomization and finish with the end of the In-hospital Follow-up Period (ie, up to the time of death / hospital discharge / Day 30, whichever occurs first).

All AESIs are identified based on the respective checkbox in the eCRF.

An overview summary of treatment-emergent SAEs and AESIs, including number and percentages of subjects as well as the number of events, with subcategories of related and not related, will be provided including the following:

- Any SAE or AESI.
- Any SAE.
- Any AESI, with subcategories by type of AESI.
- Any related AESI, with subcategories by type of AESI.
- Related SAEs.
- Any SAE or AESI Resulting in Death.
- Any AESI Resulting in Death.
- Any SAE or AESI Leading to Discontinuation of Study Treatment.
- Any SAE Leading to Discontinuation of Study Treatment.
- Any AESI Leading to Discontinuation of Study Treatment.
- Any SAE or AESI Leading to Dose Interruption.
- Any SAE Leading to Dose Interruption.
- Any AESI Leading to Dose Interruption.
- Any SAE or AESI Leading to Withdrawal from the Study.
- Any SAE Leading to Withdrawal from the Study.
- Any AESI Leading to Withdrawal from the Study.
- SAEs by Maximum Severity.
- AESIs by Maximum Severity.

Where not integrated in the overall overview in the above, additional descriptive tables will be generated by treatment arm, including number and percentages of subjects and the number of events, to have the following summaries:

- Number and percentages of subjects with TEEs by relationship and overall.
- Number and percentage of subjects with AESI, by type of AESI and Relationship (related, unrelated, and overall), including number of events.
- Number and percentage of subjects with AESI leading to death, by type of AESI, and number of events.
- Treatment-emergent Serious Adverse Events by SOC and PT.
- Serious Adverse Events Resulting in Death by SOC and PT.
- Study Treatment-related Serious Adverse Events by SOC and PT.
- Serious Adverse Events Leading to Discontinuation of Study Treatment by SOC and PT.
- Serious Adverse Events Leading to Withdrawal from the Study by SOC and PT.
- Serious Adverse Events by SOC, PT, and Maximum Severity.
- Adverse Events Leading to Death by Primary Cause of Death.

The following listings will be generated:

- SAEs.
- Fatal AEs.
- AEs leading to study Withdrawal.
- AESIs.

11.2.1 Adverse Events of Special Interest

The following AESIs up to 30 days after randomization will be evaluated in additional detail:

- 1) TEEs, symptomatic or asymptomatic, venous, or arterial (eg, deep vein thrombosis, pulmonary embolism, stroke, and myocardial infarction)
- 2) Other AESIs; namely
 - ARDS.
 - Multiple organ failure.
 - AKI requiring renal replacement therapy (dialysis, hemofiltration, or hemodiafiltration).

The number of events, the number and percentage of subjects affected in each AEs listed above, will be presented for each treatment group. Relative risk and 95% confidence intervals for the difference between the 2 treatment arms will be included. A forest plot of the relative risk and its 95% confidence intervals for the difference will be displayed along with the percentage of AESIs in each group.

The safety variables will also be compared against the background rates mentioned in the Investigator's Brochure (Section 3). This will be a descriptive analysis, showing the background rates as well as the observed rates, and 95% confidence intervals (based on the normal approximation) in each treatment arm.

12 Interim Analyses

The schedule for interim analyses conducted for the IDMC and the stopping criteria for efficacy are described in [Section 4.5](#).

As it has been decided to stop the study early, before the first interim analysis, [Section 12.2](#) is no longer applicable.

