1.4 Potential Risks and Benefits

The following benefits and risks are of consideration in this study:

Benefits

1. **There is the potential for improved survival** in patients who have traumatic injury, with confirmed or suspected acute major bleeding and / or predicted to receive a large volume blood product transfusion.
2. **There is the potential for decreased transfusion of blood products**, including RBCs, FFP, whole blood, cryoprecipitate, intraoperative salvaged (cell-saver) blood, and platelets, with reduction of associated risks, eg, transfusion reactions including

transfusion-associated circulatory overload and transfusion-related acute lung injury or transmission of infectious agents [CSL, 2018].

3. **There is the potential for decreased complications**, including decreased length of stay in the intensive care unit (ICU) and hospital and decreased number of days on mechanical ventilation.

Risks

1. **There is an increased risk of acute thromboembolic events (TEEs)**, including deep vein thrombosis, pulmonary embolism, ischemic stroke [including thromboembolic stroke], and myocardial infarction within 24 to 48 hours after BE1116 administration [CSL, 2018].
2. **The concurrent use of off-label prothrombotic agents (eg, recombinant activated FVIIa, Factor VIII inhibitor bypassing activity [FEIBA]) may increase the risk of TEEs** [Novo Nordisk, 2020; Baxalta, 2020].
3. **Hypersensitivity reactions** may occur [CSL, 2018].
4. **There is a low risk of transmissible infectious agents** (the PCC manufacturing process applies 2 dedicated virus reduction steps) [CSL, 2018].

Thus, the anticipated benefit-risk balance of BE1116 is considered acceptable for subjects enrolled in the study.

Refer to the IB for BE1116 for detailed information on the product's warnings, precautions, and full safety profile.

2 Study Objectives and Endpoints

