While the relative mortality trends in the first 6 hours will likely persist over time in the current study, secondary efficacy endpoints include all-cause in-hospital mortality up to 24 hours after randomization, and all-cause in-hospital mortality up to 30 days after randomization. These will reflect the durability of survival benefit, provide valuable safety information about later mortality and relevant complications, and are in line with other trauma studies, such as the PROPPR study [\[Holcomb et al, 2015; Fox et al, 2017\]](#). An earlier time to hemostasis was found to be independently associated with a decreased incidence of 30-day mortality, AKI, ARDS, multiple organ failure, and sepsis in 408 bleeding trauma patients, indicating that the benefits of an earlier time to hemostasis are reflected in a number of outcomes, including mortality up to 30 days [\[Chang et al, 2019\]](#).

Safety data collected in the in-hospital period after randomization (up to the time of death, hospital discharge, or 30 days, whichever occurs first; if subject is discharged alive prior to 6 hours, then the subject will be followed up to assess 6-hour survival status, SAEs, and AESIs) will allow the monitoring of AESIs and SAEs, which will be assessed for relatedness to the IP. TEEs are a defined AESI in this study because they are an identified important risk associated with use of BE1116. The other AESIs (ARDS, multiple organ failure, and AKI requiring renal replacement therapy) have been selected based on their importance in trauma

study populations. Nonserious adverse events (AEs) (other than AESIs) will not be collected in this study, because BE1116 has an established safety profile from more than 20 years of postmarketing experience in more than 45 countries, as well as from 10 clinical studies. In the current study, there will be a short duration of exposure (single dose), and the dosing range falls within that used in current clinical practice and in previous clinical studies.

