4	Serious adverse events (SAEs) considered related to IP	During the primary hospital stay only, within the 30 days after randomization: 
 • Number and proportion of subjects with SAEs considered related to IP by treatment (BE1116 or placebo)

Objectives	Endpoints	Summary Measure(s)
4	
Adverse events of special interest (AESIs):
 
 • Thromboembolic events (TEEs), symptomatic or asymptomatic, and arterial or venous (eg, deep vein thrombosis, pulmonary embolism, ischemic stroke [including thromboembolic stroke], myocardial infarction) • Acute respiratory distress syndrome (ARDS) • Multiple organ failure • Acute kidney injury (AKI) requiring renal replacement therapy (dialysis, hemofiltration, or hemodiafiltration) 
Note: superficial thromboses will not be included as AESI
	
 • TEEs: Number and proportion of in-hospital overall and related TEEs up to 30 days after randomization by treatment (BE1116 or placebo) • Number and proportion of subjects with the following: 
 ○ ARDS ○ Multiple organ failure ○ AKI requiring renal replacement therapy
Exploratory		
1	Transfusion of blood products	Number of units of blood product transfused before arrival at the hospital through the first 24 hours after randomization, overall and by type of product by treatment
2	Ventilator-free days	Number of ventilator-free days during the primary hospital stay up to 30 days after randomization, by treatment
2	Intensive care unit (ICU)-free days	Number of ICU-free days during the primary hospital stay up to 30 days after randomization, by treatment
2	Hospital-free days	Number of hospital-free days up to 30 days after randomization, by treatment

Objectives	Endpoints	Summary Measure(s)
3#	Infusion of tranexamic acid	Amount of tranexamic acid infused in milligram (mg) before arrival at the hospital through the first 24 hours after randomization, overall and by treatment
4#	Death due to hemorrhagic shock/exsanguination	Difference in proportion of deaths that are due to hemorrhagic shock/exsanguination in-hospital in the BE1116 arm compared with the placebo arm up to 30 days after randomization, as estimated by a Bayesian logistic regression model

*In-hospital mortality will only be recorded and assessed for the primary hospitalization.

#Additional endpoints not defined in the CSP but added in the SAP.

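### The only final TEE relative risk with a confidence interval pools arterial with venous and symptomatic with asymptomatic events; adding arterial and venous rows would be a cheap improvement

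*SAP*

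**What the plan says.** Protocol 3.3.1 explains why these events are singled out: "TEEs are a defined AESI in this study because they are an identified important risk associated with use of BE1116". Protocol 1.4 also lists them first among the risks.

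SAP 11.2.1 promises a more detailed look at the AESIs. Its TEE entry is one item: "TEEs, symptomatic or asymptomatic, venous, or arterial (eg, deep vein thrombosis, pulmonary embolism, stroke, and myocardial infarction", where the diagnoses are bracketed examples. For the items on that list, "The number of events, the number and percentage of subjects affected in each AEs listed above, will be presented for each treatment group", and "Relative risk and 95% confidence intervals for the difference between the 2 treatment arms will be included". A forest plot of the relative risks follows.

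The other final TEE outputs stop at the same level:
- SAP Table 1 (Section 4.1): "TEEs: Number and proportion of in-hospital overall and related TEEs up to 30 days after randomization by treatment".
- SAP 11.2: "Number and percentages of subjects with TEEs by relationship and overall".
- SAP 11.2: "Number and percentage of subjects with AESI, by type of AESI and Relationship (related, unrelated, and overall), including number of events".

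SAP 11.2 also plans by-arm tables by system organ class and preferred term, but only for SAEs (all treatment-emergent, fatal, related, by maximum severity, and those leading to discontinuation or withdrawal). AESIs are listed by subject. Protocol 9.6.2 has an AESI that meets the SAE definition marked as serious.

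**The concern.** The pooled category joins events of very different clinical weight, from a deep vein thrombosis without symptoms to a stroke. Its relative risk is a weighted result in which the commonest component dominates. If the product raised arterial events only, the one TEE estimate that carries an interval would be pulled toward 1.

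The other displays repair this only in part. Serious arterial events would be spread over several preferred terms, with no line that adds them up. Nonserious TEEs enter the pooled relative risk, but no table shows what kind of event they were. A reader of the study report could not tell from a summary table whether a pooled estimate near 1 means no effect on either component, or an arterial excess among many unaffected venous events.

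**Working it through.** **No plan figure to reproduce.** Neither document states a TEE rate, an arterial/venous mix or a detectable relative risk for safety. All rates below are assumptions.

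**Inputs from the documents**
- Allocation is 1:1 (SAP 4).
- The 1000-subject safety review took place, and the study stopped before the 2000-subject interim (SAP 4.5 and 12). That gives roughly 500 to 1000 per arm; I use 500, 750 and 1000.
- The estimate is a relative risk with a 95% interval (SAP 11.2.1). The SAP does not name the interval method; I use the usual log relative risk interval.

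**Formulas.** With venous risk v and arterial risk a, independent within a subject, and each subject counted once:
- pooled risk p = 1 − (1 − v)(1 − a)
- SE of log RR = √[(1 − p₁)/(n p₁) + (1 − p₀)/(n p₀)]
- interval = RR × exp(± 1.96 SE)

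**Main illustration: venous 8% in both arms, arterial 1% (placebo) v 3% (BE1116)**
- Placebo pooled: 1 − 0.92 × 0.99 = 0.0892
- BE1116 pooled: 1 − 0.92 × 0.97 = 0.1076
- Pooled RR = 0.1076 / 0.0892 = 1.21; arterial RR = 0.03 / 0.01 = 3

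At 750 per arm, with counts at their expected values:
- Pooled SE = √(0.8924/80.7 + 0.9108/66.9) = 0.157; interval 0.89 to 1.64
- Arterial SE = √(0.97/22.5 + 0.99/7.5) = 0.418; interval 1.32 to 6.81

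**How often the 95% interval lies wholly above 1** (binomial counts simulated, 200,000 trials per row):

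| Venous, placebo v BE1116 | Arterial, placebo v BE1116 | Per arm | Pooled RR | Pooled | Arterial |
|---|---|---|---|---|---|
| 8% v 8% | 1% v 3% | 500 | 1.21 | 16% | 59% |
| 8% v 8% | 1% v 3% | 750 | 1.21 | 22% | 79% |
| 8% v 8% | 1% v 3% | 1000 | 1.21 | 28% | 90% |
| 2% v 2% | 1% v 3% | 750 | 1.66 | 49% | 79% |
| 8% v 8% | 1% v 2% | 750 | 1.10 | 9% | 33% |
| 8% v 12% | 1% v 1.5% | 750 | 1.49 | 77% | 12% |

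The first four rows show dilution, which is smaller when venous events are uncommon. The fifth shows that a doubling from 1% to 2% would usually be missed even with an arterial row. The last row is the reverse case: both components rise 1.5-fold, the pooled RR is (1 − 0.88 × 0.985) / 0.0892 = 0.1332 / 0.0892 = 1.49, and pooling is much the better measure.

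**The case against.** A reader might infer that the SAP compares the arms on thromboembolism only through one pooled count, so that an arterial excess would be hidden. The documents do not support that.

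- **Serious events are shown by arm.** Most strokes, myocardial infarctions and pulmonary emboli should meet an SAE criterion in Protocol 9.1.2. Once marked serious, they belong in the by-arm SAE tables by preferred term. In the main illustration at 750 per arm, about 7.5 v 22.5 arterial events would be expected, and those that are serious would be visible there. What is missing is a total and an interval.
- **Nonserious TEEs are displayed.** They are in the AESI listing. They lack a summary by type, and this gap probably falls mainly on venous events.
- **The IDMC saw more detail.** SAP 12.1 has the safety events shown individually as well as in categories, and individual events set against background rates. The 500- and 1000-subject reviews took place. This concerns monitoring, not the outputs for the study report.
- **The pooled category is the protocol's own endpoint** (Protocol 2.2.2 and 10.3.3), and SAP 4.1.2 rules out formal testing of SAEs and AESIs. The detection percentages above therefore measure how informative an interval is; they are not the power of a planned test.
- **Pooling is not always the weaker choice**, as the last table row shows.
- **Site differences in looking for silent clots do not favour an arm**, since randomization is stratified by site and staff are blinded. They can only add noise or dilution.

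The SAP wording about each event listed above could also be read to include the bracketed diagnoses. The tables by type of AESI point the other way. If the wider reading is meant, the SAP should say so.

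All of this stands. It removes any claim that an arterial signal would go unseen. The remaining gap is that no estimate with an interval separates arterial from venous events, and no table shows nonserious TEEs by type.

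**Conclusion.** The point holds as a limited improvement. For the product's identified important risk, the only final estimate with an interval is pooled, and an excess confined to arterial events would be diluted in it. Under the assumed 8% venous and 1% v 3% arterial rates, the relative risk falls from 3 to about 1.21. The chance that the interval lies above 1 falls from 59% to 16% at 500 per arm and from 79% to 22% at 750.

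These sizes rest on assumed rates, independence of the two event types, no venous effect, and a Safety Population of about the size randomized. With a proportional rise in both components the ranking reverses (77% pooled v 12% arterial at 750 per arm), so the split should supplement the pooled row and not replace it. The plan contains no error here, and the point concerns analysis and reporting only, not clinical management.

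**What to change.** In SAP 11.2.1:
1. Keep the pooled TEE row.
2. Add one row for arterial TEEs and one for venous TEEs, each with subjects, events, relative risk and 95% interval, in both the table and the forest plot.
3. Add a by-arm table of all AESI-flagged TEEs, serious and nonserious, by preferred term.
4. Fix the arterial/venous grouping of preferred terms at the Planned Analysis Review Meeting, before database lock and unblinding.
5. Label the new rows descriptive and unadjusted, and note that small arterial excesses will remain imprecise (1% v 2%: about 33% at 750 per arm).

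The cost is two rows and one table from events already coded in MedDRA, plus a short grouping list. The downside is a few more unadjusted contrasts, some on sparse counts.

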10.3.2 Efficacy Analyses

10.3.2.1 Primary Efficacy Endpoint Analyses

A Bayesian logistic regression will be used to compare all-cause mortality rate during the first 6 hours after randomization between the BE1116 and placebo arms, in the ITT Population.

Hypotheses:

Null Hypothesis (H_0): The all-cause 6-hour mortality rate in BE1116 is no better than control.

$$p_{kcentra} - p_{control} \geq 0$$

Alternative Hypothesis (H_1): The all-cause 6-hour mortality rate in BE1116 is lower than control.

$$p_{kcentra} - p_{control} < 0$$

Let y_i be the outcome of all-cause 6-hour death (1 = yes, 0 = no), the model is:

$$y_i \sim Bernoulli(p_i)$$

$$\text{logit}(p_i) = \beta_0 + \beta_1 \text{treatment}_i$$

where p_i is the probability of all-cause 6-hour mortality for subject i treatment intervention. The coefficient β_0 is the effect of placebo on the primary outcome in the logit scale. The

coefficient β_1 is the treatment effect of BE1116 over placebo on the primary outcome in the log OR scale. While this model gives direct estimates of ORs, the absolute risk differences (primary outcome of interest) will be derived using posterior draws from the coefficients. We assume independent normal prior distributions for the regression coefficients:

$$\beta_0 \sim \text{Normal}(\mu_0, \tau_0^2)$$

$$\beta_1 \sim \text{Normal}(\mu_1, \tau_1^2)$$

where, μ s and τ s are respectively the means and standard deviations of distributions.

For all interim and final analysis, the following noninformative priors are used:

$\beta_0 \sim \text{Normal}(0, 10^2)$, $\beta_1 \sim \text{Normal}(0, 1^2)$. These priors are centered at zero, which for β_1 corresponds to a priori no intervention effect. This noninformative prior allows considerable uncertainty; the 95% interval for β_1 on the OR scale ranges from 0.14 to 7.1 while avoiding unreasonable values.

The study will be considered a success and primary objective considered met if the posterior probability $\text{Prob}(p_{k\text{centra}} - p_{\text{control}} < 0 | \text{data})$ of lower all-cause 6-hour mortality in the BE1116 arm compared with the placebo arm is greater than the success threshold.

Interim analyses will occur when 1/4 (2000), 1/2 (4000), and 3/4 (6000) of the targeted 8000 subjects have data for the primary outcome. A group sequential approach will be utilized (see [Section 10.3.4](#)).

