4.1.2 Secondary Endpoints Hypotheses

The hypotheses for the secondary efficacy endpoints are the same as that for the primary hypothesis. These hypotheses will be formally tested in a sequential order if the primary efficacy endpoint reaches success. There will be no formal statistical testing for the occurrence of SAEs and AESI.

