4.5 Interim Analyses

This section briefly describes the interim analyses as originally planned. In October 2024, it was decided by the sponsor to stop the study early. Therefore, the interim analyses will not take place and only a final analysis with a reduced sample size will be conducted.

The IDMC meetings were scheduled to review unblinded data for both safety and efficacy according to the planned interim analysis schedule shown in Table 2. The safety reviews for 500 and 1000 subjects enrolled took place prior to study stop. Unblinded data for safety were provided to the IDMC.

Table 2 **Planned IDMC Reviews**

IDMC Meeting Type	Number of Subjects Enrolled
Safety review	500
Safety review	1000
Scheduled Interim Analysis 1 – Safety and futility review*	2000
Safety review*	3000
Scheduled Interim Analysis 2 – Safety, efficacy, and futility review*	4000
Safety review*	5000
Scheduled Interim Analysis 3 – Safety, efficacy, and futility review*	6000

IDMC = Independent Data Monitoring Committee; *=review/analysis will not take place due to early study termination.

Interim Efficacy and Futility Analyses: Interim futility analyses were to be conducted by the IDMC when approximately 25%, 50% and 75% of patients have been enrolled. For the originally planned stopping criteria and their justification refer to SAP Version 1.0 or Section 10.3.4 of the CSP.

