12.1 Safety Analyses and Stopping Rules

The subjects participating in this study are expected to have a high mortality rate and have many significant complications. Given that BE1116 has the potential to reduce mortality, any specific predefined stopping rule for safety reasons for anything other than mortality is inappropriate. The protocol has an efficacy based stopping rule that stops the trial for futility and will stop the trial if there is significantly more mortality in the study arm than in the treatment arm. Hence, this futility stopping rule also serves as a safety stopping rule. In addition, the IDMC will consider other adverse events combined with mortality endpoints as described below.

Commensurate with its mandate to review ongoing safety data, the IDMC will monitor all-cause mortality up to 30 days, adverse events including SAEs and AESI, as well as other safety data with the objective of ensuring the safety of study participants. Upon review of the safety data, the IDMC may recommend stopping the study due to significant safety issues or propose modifications to the study. Partially unblinded data (treatment arms are masked as A and B) will be provided for safety only IDMC. If significant difference is observed between two arms which could result in pause or termination of the study, the actual treatment arms will be released to IDMC.

Beginning at the time of 500 completed subjects, and at every regularly scheduled IDMC review thereafter, the Independent statistician will perform statistical testing for the following safety variables of interest up to 30 days after hospital arrival:

- 1) All-cause in-hospital mortality up to 30 days
- 2) SAEs with fatal outcome
- 3) In-hospital TEEs, symptomatic or asymptomatic, venous, or arterial (eg, deep vein thrombosis, pulmonary embolism, ischemic stroke, and myocardial infarction)
- 4) Other in-hospital AESIs; namely
 - ARDS
 - Multiple organ failure
 - AKI requiring renal replacement therapy (dialysis, hemofiltration, or hemodiafiltration)

A Fisher's exact test will be used to detect any differences in proportions of the above mentioned safety events between treatment and placebo arms at each predefined IDMC review. Four independent analyses will be performed for each safety variable of interest.

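### For AESI categories with few events, the normal-approximation intervals planned in SAP 11.2.1 would fall short of 95% coverage and set the upper limit too low; a Wilson or Clopper-Pearson interval avoids this at no real cost.

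*SAP*

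**What the plan says.** SAP 11.2.1 (Adverse Events of Special Interest) lists four categories: thromboembolic events (TEEs), ARDS, multiple organ failure, and AKI requiring renal replacement therapy. Their rates are to be set against background rates held in the Investigator's Brochure. The SAP states the status of this comparison plainly: "This will be a descriptive analysis, showing the background rates as well as the observed rates". Each observed rate carries "95% confidence intervals (based on the normal approximation) in each treatment arm". The SAP does not say which normal-approximation interval is meant, and it gives no rule for a category with no events or very few.

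SAP 4.1.2 adds: "There will be no formal statistical testing for the occurrence of SAEs and AESI".

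Neither document gives a background rate or an expected AESI rate. The nearest statement, in SAP 12.1, is qualitative: "The subjects participating in this study are expected to have a high mortality rate and have many significant complications". No final sample size is given either, but the documents bracket it. SAP 4.5 reports that "The safety reviews for 500 and 1000 subjects enrolled took place prior to study stop". The opening of SAP Section 12 begins: "As it has been decided to stop the study early, before the first interim analysis". Protocol 10.3.2.1 fixes the timing of that first look: "Interim analyses will occur when 1/4 (2000), 1/2 (4000), and 3/4 (6000) of the targeted 8000 subjects".

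**The concern.** Unqualified, a normal-approximation interval for a proportion usually means the Wald interval: the observed rate plus or minus 1.96 estimated standard errors. The standard error is computed from the observed rate, so a sample that happens to contain few events gives both a low estimate and a short interval. Coverage then drops below 95%, and the misses fall mainly on one side, with the true rate above the upper limit. The lower limit can be negative, and with no events the interval has zero width.

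The purpose of the display is to let a reader judge whether an arm's rate is compatible with background. If a category is rare, and the arm's true rate equals the background rate, a Wald interval will too often lie wholly below background and make the arm look safer than it is. TEEs are an identified important risk of the product (Protocol 3.3.1), so the direction of the error matters even in a descriptive table.

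**Working it through.** **Inputs**

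- Nominal level: two-sided 95% (SAP 11.2.1). This is the only figure the plan states here. There is no planned rate, count or interval to reproduce.
- Subjects per arm: *assumption*, about 500 to 1000. At least 1000 were enrolled, the stop came before the look planned at 2000, and allocation is 1:1. The Safety Population contains dosed subjects only, so it may be slightly smaller.
- True AESI rate: *assumption*, since none is given. A range of 0.5% to 10% is shown.

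**Formulas**

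- Wald: p̂ ± 1.96·√(p̂(1−p̂)/n).
- Wilson: [p̂ + z²/2n ± z·√(p̂(1−p̂)/n + z²/4n²)] / (1 + z²/n), with z = 1.96.
- Exact coverage at true rate p: the sum of binomial(n, p) probabilities over every count x whose interval contains p.

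**One case in full: n = 500, true rate 1% (5 events expected)**

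Wald upper limits for 0, 1, 2 and 3 events are 0, 0.59%, 0.95% and 1.28%. The interval therefore misses 1% from below whenever there are 2 events or fewer:

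P(0) + P(1) + P(2) = 0.66% + 3.32% + 8.36% = 12.3%, against a nominal 2.5%.

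It misses on the other side (12 or more events) with probability 0.5%. Coverage is 87.1%. With Wilson, the upper limit at 1 event is 1.12%, so only zero events is a miss on the high-rate side (0.7%), and coverage is 96.2%.

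**Exact Wald coverage (%)**

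| True rate | n = 500 | n = 650 | n = 800 | n = 1000 |
|---|---|---|---|---|
| 0.5% | 91.4 | 83.4 | 90.6 | 87.1 |
| 1% | 87.1 | 88.3 | 89.4 | 92.7 |
| 2% | 92.8 | 94.1 | 94.6 | 95.0 |
| 3% | 92.3 | 93.9 | 93.4 | 93.5 |
| 5% | 93.2 | 94.0 | 94.3 | 94.2 |
| 10% | 94.3 | 94.7 | 95.2 | 95.3 |

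Coverage of a discrete variable moves in steps, so values between the tabulated rates can differ. At n = 500 it averages 93.7% over rates from 2% to 5%, with a lowest value of 90.8%. Over 0.5% to 1% it averages 89.3%, with a lowest value of 79.3%.

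At the rates and arm sizes in the table, Wilson coverage is 93.1% to 96.4% and Clopper-Pearson coverage is at least 95.1%.

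**What a reader would see at n = 500**

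| Events | Wald | Wilson | Clopper-Pearson |
|---|---|---|---|
| 0 | 0 to 0 | 0 to 0.76% | 0 to 0.74% |
| 2 | −0.15% to 0.95% | 0.11% to 1.45% | 0.05% to 1.44% |
| 5 | 0.13% to 1.87% | 0.43% to 2.32% | 0.33% to 2.32% |
| 10 | 0.77% to 3.23% | 1.09% to 3.64% | 0.96% to 3.65% |
| 50 | 7.4% to 12.6% | 7.7% to 12.9% | 7.5% to 13.0% |

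The chance of no events at n = 500 is 8% at a 0.5% rate, 0.7% at 1% and about 0.004% at 2%.

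**The case against.** The strongest reply is that nothing in the documents shows any displayed category to be rare. The only expectation stated is of many complications, and Protocol 3.3.1 says ARDS, multiple organ failure and AKI with renal replacement were chosen for their importance in trauma. At 5% and above, every tabulated Wald coverage is within 2 points of nominal. At 2% and n = 650, Wald (94.1%) is closer to 95% than Wilson (93.4%). This stands, and it makes the point conditional on rates the documents do not give.

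A second reply is that nothing rests on these intervals. The observed and background rates do not depend on the interval method, event counts are shown alongside, and the randomized comparison of AESIs is made through the relative risk in SAP 11.2.1. The IDMC reviews in SAP 12.1 use Fisher's exact test, which copes with sparse counts. This also stands.

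A third is that the Wald form is inferred. Wilson's interval is also built on a normal approximation and does not collapse at zero. That is true, but it is a reason to name the form.

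A reader might go further in two ways that the documents do not support. One is to cite related-only events or individual TEE types as the rare rows. SAP 11.2.1 lists TEEs as one category, with types given only as examples, and related events are tabulated in SAP 11.2 as counts and percentages; neither is established as a row of this display. The other is to extend the criticism to the relative-risk intervals. The SAP names no method for them, and no defect has been shown there.

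**Conclusion.** The point holds as a minor one. If a displayed category has a true rate of about 1% or lower, the Wald interval covers 87-93% at 1% and 83-91% at 0.5% instead of 95%. Its upper limit is too low, and it gives [0, 0] when there are no events. At the tabulated rates of 2% and above, coverage is about 92-95% and the practical effect is small.

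This rests on three assumptions: that the SAP means the Wald form, that there are about 500 to 1000 subjects per arm, and that some category may prove rare. The last cannot be settled from the documents.

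A reader might infer that the comparison with background rates is itself wrong. It is not: the comparison is descriptive, the rates being compared are unaffected, and no success, stopping or safety decision uses these intervals. What can mislead is the interval attached to a sparse category.

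**What to change.** In SAP 11.2.1, replace the parenthetical reference to the normal approximation with *Wilson score (or Clopper-Pearson) intervals* for each arm's rate. Apply the chosen method to all four categories so that it does not depend on the counts observed.

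The cost is one phrase in the SAP and one option in the frequency procedure, with no new data. Clopper-Pearson is slightly wider than needed; Wilson has essentially no downside. The change should be made before database lock, with the other analysis decisions.
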